Abdominal wound dehiscence (also referred to as 'evisceration' or 'fascial dehiscence'). Defined as an unintended acute wound failure at the level of the fascia and a postoperative complication after primary closure of a laparotomy incision.

Degree of contamination during surgery

Clean: an incision in which no inflammation is encountered in a surgical procedure, without a break in sterile technique, and during which the respiratory, alimentary and genitourinary tracts are not entered

Clean-contaminated: an incision through which the respiratory, alimentary or genitourinary tract is entered under controlled conditions but with no contamination encountered

Contaminated: an incision undertaken during an operation in which there is a major

break in sterile technique or gross spillage from the gastrointestinal tract, or an incision in which acute, non-purulent inflammation is encountered. Open traumatic wounds that are more than 12 to 24 hours old also fall into this category

Dirty: An incision undertaken during an operation in which the viscera are perforated or when acute inflammation with pus is encountered during the operation (for example, emergency surgery for faecal peritonitis), and for traumatic wounds where treatment is delayed, and there is faecal contamination or devitalised tissue present.

Early abdominal wound failure. Defined as surgical site infection, surgical site occurrence or abdominal wound dehiscence diagnosed within 30 days postoperatively.

Incisional hernia. Defined by the European Hernia Society as "any abdominal wall gap with or without a bulge in the area of a postoperative scar perceptible or palpable by clinical examination or imaging".

Late abdominal wound failure. Defined as surgical site infection in presence of foreign body material or incisional hernia at one year postoperatively.

SSI: Surgical Site Infection. Defined by the CDC (Centers for Disease Control and Prevention) as infections related to a surgical procedure that occur near the surgical site within 30 days following surgery (or up to 1 year following surgery where synthetic implants are involved).

SSO: Surgical Site Occurrence. Defined as: wound cellulitis, non-healing incisional wound, skin or soft tissue ischemia, skin or soft tissue necrosis, serous wound drainage, stitch abscess, seroma, hematoma, infected or exposed mesh, surgical site infection, abdominal wound dehiscence.

INTRODUCTION

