- 4. What are the effects of SSI prevention measures on the incidence of early and late abdominal wound failure?
- 5. What is the impact of a minimally invasive technique vs. open technique on the incidence of early and late abdominal wound failure?
- 6. What is the impact of early and late abdominal wound failure on the patient?
- 7. What is the impact of early and late abdominal wound failure on the duration of postoperative stay and the number of outpatient visits and unscheduled hospital visits?
- 8. What are the early and late abdominal wound failure associated costs (eg, hospital/ICU stay, unscheduled hospital visits and patient reported expenses)?
- 9. Which risk scores will have the highest predictive value for our primary outcomes within this cohort?

Summary of the cohort study key objectives

Short term:

Assessing the different practices of wound closure and surgical site prevention globally

Assessing the effect of wound closure and surgical site infection prevention practices on the incidence of abdominal wound failure at 30 days.

Longer-term:

Early phase: 30 days to 90 days
Assessing the different practices of abdominal wound closure and surgical site prevention globally and their effect on wound healing, SSI, patient recovery and return to normal function.

Later phase: 90 days to 1 year
The incidence of abdominal wound failure, including the development of incisional hernia.

Overall:

Exploring the relationship between early adverse wound outcomes and longer-term patient-reported incisional hernia occurrence.

Comparison of quality of life for patients with and without wound healing issues and/or incisional hernia.

Key outcome measures

Short term:

Methods of Wound Closure:

- Types and techniques of fascial, subcutaneous and skin closure
- Incidence and types of mesh use
- Use of SSI Prevention measures
- Incidence of abdominal wound failure at 30 days
- Length of postoperative stay
- Reoperations within 30 days
- 30-day mortality
- SSI diagnosis or management requiring ICU admission
- Unplanned readmissions within 30 days
- Need for interventional radiology procedures within 30 days
- Abdominal wound dehiscence within 30 days

Long-term:

Patient-reported outcomes and quality of life from 30 days to 1 year post-operation

At all time points:

- EQ5D-5L
- SF-12

Early phase [wound healing / SSI / return to normal function]: 30 days to 90 days

- Bluebelle wound healing questionnaire at 30 days

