- Patient reported Wound Recovery PROM - outpatient visits, unplanned hospital visits within 90 days, wound healing, return to work, satisfaction with wound at 30 days
- Repeat the Patient reported Wound Recovery PROM at 60 days and 90 days if wound is not fully healed at these time points

Late phase [wound integrity, reintervention, incisional hernia]: 90 days to 1 year

- Clavien Dindo classification at 30 days
- Surgical site occurrences at 30 days
- ESCP Incisional hernia PROM at 90 days, 6 months, 1 year
- HerQles questionnaire at 1 year

STUDY DESIGN

International prospective cohort study.

The study will collect wound closure and SSI prevention measures employed, and short-term clinical outcomes up to 30 days and longer-term patient-reported outcomes.

Study Timelines

- The cohort study, will open within one month of being approved.
- Participating sites must have started recruitment within 3 months of the study being approved.
- The study is anticipated to close to recruitment in mid-2025.

ELIGIBILITY

Hospital inclusion criteria

Any hospital or surgical unit performing elective and/or emergency abdominal general and colorectal surgery.

Participating sites will be expected to recruit at least 10 consecutive eligible patients within a 4-week period.

At hospital level, data completeness of 95% will be required.

Patient eligibility

Inclusion criteria

- Adult patients (age 18 years and above) undergoing general or colorectal surgical procedures
- Elective (planned admission), expedited (within two weeks), or emergency (unplanned admission) surgery.
- General and colorectal procedures using any type of abdominal incision measuring at least 5 cm (including extraction sites).
- Able to give written informed consent

*For those patients who do not speak the national language of the country in which they are recruited for participation, normal hospital policies for translation to facilitate participation will be followed.

Exclusion criteria

- Patients undergoing incisional, ventral, umbilical, and inguinal/femoral hernia repair
- Simultaneous hyperthermic intraperitoneal chemotherapy (HIPEC) and/or cytoreductive surgery
- Stoma reversal without additional laparotomy incision
- Anyone who does not have an email address or who does not have access to the internet or a smart device.

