Note: Each individual patient should only be included once. Following the index procedure (i.e. the procedure for study inclusion), patients undergoing additional procedures within the study window should not be included for a second time. Data on these additional procedures will be captured as part of patient follow-up.

Selection bias

Selection bias will be closely monitored by the Study Management Group. Study coordinators will regularly liaise with site Principal Investigators to ensure that all eligible patients are entered consecutively into the study. Recruitment rates will be monitored across individual sites and clarification will be sought in case of a drop in recruitment that might indicate that eligible patients were not included.

PATIENT IDENTIFICATION AND CONSENT

All consecutive adult patients who fulfil the eligibility criteria should be included. As this is an international study, each participating country and hospital will decide how best to identify and approach eligible patients. It is anticipated that potential participants may be identified as described below.

Potential participants may be identified:

- Pre-operatively:
 - Surgical outpatient clinics (e.g. when the patient is being booked for elective surgery)
 - Planned theatre lists (e.g. at the time of admission for surgery)
 - Emergency surgical admissions (e.g. at the time that a decision to operate is made)
- Intra-operatively
 - By operative team
- Post-operatively prior to discharge:
 - By the operating surgeon

SCREENING

The WOLVERINE Screening Log will be held on the REDCap data capture system. Each potential participant will be recorded by the site and a REDCap id number generated for every record entered. This REDCap ID number will then be used for those patients who are eligible and provisionally agree to enter the cohort study.

No specific screening visits or other screening procedures are planned.

INITIAL APPROACH TO PATIENT

Potential participants will be approached by either:

- The senior operating surgeon
- Any doctor involved in the patients' care (e.g. surgeon in training)
- Clinical nurse specialist (depending on local regulations)

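### Late wound failure is not limited to new hernia at the index incision, so an existing hernia left unrepaired at entry counts as an outcome

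*Protocol*

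**What the plan says.** Under Eligibility, the protocol admits "Adult patients (age 18 years and above) undergoing general or colorectal surgical procedures" whose operation meets the incision criterion, "General and colorectal procedures using any type of abdominal incision measuring at least 5 cm (including extraction sites". Urgency class and written consent are the other inclusion criteria. The exclusion that bears on hernia is "Patients undergoing incisional, ventral, umbilical, and inguinal/femoral hernia repair". It depends on having a repair, not on having a hernia.

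The list of definitions describes incisional hernia, in the words of a society definition, as "any abdominal wall gap with or without a bulge in the area of a postoperative scar". Late abdominal wound failure is defined there as incisional hernia at one year, or surgical site infection where foreign material is present. Neither entry mentions new onset or the index incision.

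The key objectives give the later-phase target as "The incidence of abdominal wound failure, including the development of incisional hernia", and the main research question speaks of hernia formation.

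The schedule of events gives the incisional hernia questionnaire at 90 days, 6 months and 1 year. The Study Follow-up section also lists it at 30 days. Every listed time is after surgery, and the same section states that the clinical team has no role after day 30. The Analysis Plan summarises outcomes in the audit and cohort populations and names no at-risk subset.

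**The concern.** The objective is an incidence, but the definition that decides what counts is a state at one year. A patient with an old incisional hernia who has, for example, a bowel resection without repair meets the entry criteria, still has a gap at a postoperative scar a year later, and satisfies the definition of late failure. Nothing stated in the protocol separates that patient from one whose index closure failed.

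The main research question relates closure materials and techniques to early and late failure, and the Background says the data will serve as a benchmark for a future interventional study. An incidence inflated by prevalent cases would carry into both. The data needed to remove those cases must be collected at entry. They cannot be recovered reliably from questionnaires first sent after surgery.

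**Working it through.** **Does the text let a prevalent hernia through?**

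1. Entry: no criterion requires an abdominal wall free of hernia. The repair exclusion removes part of the group. Unrepaired hernias remain.
2. Outcome: the hernia definition is met by a gap at any postoperative scar, whenever it arose.
3. Timing: the hernia questionnaire has no pre-operative administration.
4. Denominator: none is restricted to patients at risk.

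All four steps hold on the protocol's own wording.

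**How large could the effect be?** The protocol gives no hernia incidence or prevalence for this population. The 1,000 patients are a recruitment projection, so there is no planned figure to reproduce. The following inputs are assumptions:

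- I = true one-year incidence among patients hernia-free at entry, 10%.
- q = share entering with an unrepaired hernia that the questionnaire later picks up, 3%, 5% or 8%.

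Reported proportion = q + (1 − q) × I.

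| q | Calculation | Reported | Ratio to 10% | Prevalent share of reported cases |
|---|---|---|---|---|
| 3% | 0.03 + 0.97 × 0.10 | 12.7% | 1.27 | 0.03 / 0.127 = 24% |
| 5% | 0.05 + 0.95 × 0.10 | 14.5% | 1.45 | 0.05 / 0.145 = 34% |
| 8% | 0.08 + 0.92 × 0.10 | 17.2% | 1.72 | 0.08 / 0.172 = 47% |

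Over a wider grid, I from 5% to 20% and q from 2% to 10%, the ratio runs from 1.08 (q = 2%, I = 20%: 21.6%) to 2.90 (q = 10%, I = 5%: 14.5%). Restricting to patients hernia-free at entry returns I in every case.

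**Closure-group comparisons.** Take two groups of 500 with the same true incidence of 10%:

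- Equal q in both groups: no false difference arises.
- q of 3% and 5%: reported 12.7% and 14.5%. A two-sided 5% test rejects in about 13% of studies.
- q of 2% and 8%: reported 11.8% and 17.2%, odds ratio 1.55. The test rejects in about 68% of studies.

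If a true difference exists and q is equal, the reported risk difference is the true one times (1 − q), so 0.97 to 0.92 of it for q of 3% to 8%.

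**Dehiscence.** The definition presupposes closure: "a postoperative complication after primary closure of a laparotomy incision". If a share r is not primarily closed and dehiscence among closed wounds is D, the reported rate is (1 − r) × D. With assumed D = 4%, r of 1% to 10% gives 3.96% to 3.60%, a relative fall of 1% to 10%. This effect is small.

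**The case against.** The strongest reply is that the intention is plain. The protocol speaks of formation, development and incidence, and the scar wording is borrowed from a diagnostic definition, not written as an analysis rule. The questionnaire text is not shown and may ask about a new bulge at the index wound. A statistical analysis plan is promised and could set the denominator, the case report form is not shown, and the work is described as hypothesis-generating. On a wide reading, the repair exclusion also removes anyone whose hernia is repaired at the same operation.

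Much of this is fair, and it limits the point. It cannot be said that a baseline hernia item is absent from the case report form, only that the protocol states none. But the stated intention is one half of the conflict and does not resolve it, and an analysis plan can exclude prevalent cases only if they were recorded at entry.

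Several stronger conclusions are tempting and are not supported:

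- A reader might infer that incision length alone decides entry. It does not; the other inclusion and exclusion criteria also apply.
- A reader might infer that a patient entering at a re-laparotomy after an operation outside the study already has the outcome. The rule "Each individual patient should only be included once" does not bar such an entry. However, early failure is failure diagnosed in the 30 days after the index operation, and a re-closed wound is again at risk. At most, re-closures are mixed with first closures.
- A reader might infer that patients left with an open abdomen cannot have the outcomes. They can still have surgical site infection and most surgical site occurrences, and only dehiscence presupposes closure. Type of fascial closure is a listed measure, so these patients are probably identifiable.
- A reader might infer that planned returns will be counted as failures of care. The protocol says that "patients undergoing additional procedures within the study window should not be included for a second time" and that later procedures are captured in follow-up. Reoperations are simply not subdivided.
- A reader might infer that existing hernias gather in the mesh or mass-closure groups. Nothing in the document shows this.

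**Conclusion.** The hernia point holds on the text. Unrepaired prevalent hernias are eligible, satisfy the definition of late failure, and are not separated from new ones by any stated assessment, although the objective is incidence. Where such patients are enrolled and report the hernia, the bias in the reported rate is upward.

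Its size is unknown. The 12.7%, 14.5% and 17.2% illustrations rest on an assumed 10% incidence, assumed prevalences of 3%, 5% and 8%, detection of every new case, and complete follow-up to one year. A spurious difference between closure groups requires prevalence to differ between them, which is possible but not shown.

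The open-abdomen and re-laparotomy questions are secondary. They call for clearer reporting groups, not for new exclusions. The hernia point should be corrected, because a later analysis plan cannot repair it without a baseline item.

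**What to change.** 1. Define the hernia component of late failure as new incisional hernia at the index incision.
2. Record at baseline any existing abdominal wall hernia and its site, from routine pre-operative notes or imaging.
3. Use patients free of hernia at the index incision site at entry as the denominator for hernia incidence, and describe prevalent cases separately.

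As a minor addition, report dehiscence and fascial-closure comparisons among patients with primary fascial closure at the index procedure, and describe open-abdomen patients separately. Report planned returns apart from other reoperations, and flag index procedures that re-open a recent laparotomy.

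Re-laparotomies should stay in. Excluding them would cut against the unselected emergency population that the protocol seeks, and against its statement that eligibility is the same in the cohort and the parallel audit. The changes above leave eligibility untouched.

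The main cost is one baseline item from existing records, some wording, and a slightly smaller hernia denominator. Under the assumed prevalences, and if every existing hernia lay at the index site, 3% to 8% of patients would leave that analysis.

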Patients will be provided with background information about the study*, including the premise of the study, patient pathways, and what their participation would involve. The patient will have an opportunity to ask questions and a written WOLVERINE Study patient information sheet (PIS) will be provided as an adjunct to this conversation.

A record of the discussion with the patient will be kept in the patient's medical notes.

*The patient-facing documents will be available in the national language of each participating country.

PATIENT CONSENT

Informed consent within the WOLVERINE cohort study will be documented in REDCap.

Wolverine Protocol IRAS: 334321

^{**}Ideally, potential participants will be identified pre-operatively.

WOLVERINE is a non-interventional study; there are no clinical interventions additional to those received as part of routine clinical care. Only routinely collected, anonymised data will be collected by the clinician at baseline and 30-days.

However, at the 30, 60, 90 days and 6-month, one-year post-op follow-up time points, patient reported outcomes will be collected remotely via REDCap, thus consent is required for the collection and analysis of this data.

Patient consent is therefore specifically sought for the permission to collect the follow-up data via the remote monitoring system and to contact the patient at the 30, 60, 90 days and 6-month, one-year post-operative follow-up time points via email or text reminders. Participants will be contacted up to three times at each timepoint to request completion of the questionnaires. Reminders will be sent via an automated email reminder from the central team at the University of Birmingham. As part of the consent process, patients will be asked to provide their email address and mobile phone number.

Process for consent for follow-up

Consent will be obtained remotely via REDCap.

Once a patient is identified as eligible, their surgeon or another member of their direct clinical care team will discuss the study with them. They will be provided with the PIS to facilitate the discussion.

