The patient will be provided with a unique patient identification number by the person discussing the study with them (this is taken from the site-specific WOLVERINE REDCap LINK SHEET provided by the study office). This unique identifier will be recorded on the WOLVERINE PIS. Eligible patients will also be provided with a generic QR code. This QR code and unique identifier will be used by the potential participants to access the REDCap-WOLVERINE system and the consent form.

The potential participant will then be asked to access the online system at a time convenient to them, i.e. they do not need to access the system whilst in hospital. Upon access of the online REDCap system, they will be asked for consent for follow-up.

This unique REDCap ID will be the only identifier used to identify the patient in any correspondence between the coordinating centre and the participating site.

*Participating sites may download the consent form as a PDF if required for the WOLVERINE Site File.

STUDY FOLLOW-UP

Follow-Up Time points

After the baseline visit, there are no further study-specific visits. All study-specific follow-up is conducted via remote reporting.

There are 5 follow-up time points: 30-, 60- AND 90-days post-surgery; 6 months and one year post-surgery.

Short-term follow-up: 30-days post-surgery

- Clinician reported:
 - o Conducted without the need for patient attendance.
 - No specific follow-up visit is mandated for participants.
 - The 30-day post-surgical outcomes form is undertaken by the clinical team, with routinely collected information from patient notes or electronic records, or other routinely collected data sources.
- Patient reported
 - Data is collected remotely from the participant via the WOLVERINE online REDCap system
 - Bluebelle wound healing questionnaire, EQ-5D5L, SF-12, the Patient reported Wound Recovery PROM QoL and the ESCP Incisional Hernia PROM.

Longer-term follow-up

At the 60-days, 90-days, 6-month and 1 year post-operative timepoints, data is collected remotely from the patient only. The following questionnaires will be requested:

- The EQ-5D5L and the SF-12 at each of the 4 timepoints.
- Bluebell wound healing questionnaire at 30 days.
- Patient reported Wound Recovery PROM at 60 days and 90 days.
- ESCP incisional hernia PROM at 3-, 6- and 12-months.
- HerQles questionnaire at 1 year

^{**}There is no clinical team involvement beyond 30-days post-surgery.

COHORT STUDY SCHEDULE OF EVENTS

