		WOLVERINE COHORT STUDY								
		Study entry	Baseline data	After Surgery	30-day follow- up	30-day PROM	60-day PROM ER DATA	90-day PROM	6-month PROM	1-year PROM
Oliveinian	Patient information		√			PROM NO FURTH	CTION AI	JOIT		
Clinician reported audit	Surgery information			>	1	NO COLLE	DAYS			
- all patients	Short-term Complications / reinterventions				✓					
Patient reported cohort	Informed consent	√								
study – only patients	Wound healing questionnaire (Bluebelle)					√				
who provide consent, recorded	Patient reported Wound Recovery PROM					1	√ if wound unhealed	√ if wound unhealed		
via online PROMS system	ESCP incisional hernia PROM							√	1	√
N.B -	HerQles questionnaire									√
IN ADDITIO N to the clinician-reported patient-level audit data	EQ-5D-5L					√	✓	√	√	√
	SF-12					√	√	√	√	√

PROMS targets for:

- 30 days -> 90 days
 - o SSI, wound healing, return to normal function, patient satisfaction
- 90 days -> one year

 wound integrity, reintervention or readmission, incisional hernia, patient satisfaction

PATIENT WITHDRAWAL

Patients are free to withdraw from the study at any point and will be made aware from the beginning of their involvement in the study that they can withdraw at any time. Participants are given details on how to withdraw from the study in the Patient Information Sheet Before the start of each follow up questionnaire patients will be asked if they are happy to continue participating in the study.

Reasons for Withdrawal

Patients are free to withdraw from participation in the study at any time upon request.

An investigator may terminate a study subject's participation in the study if:

- Any medical condition, event or situation occurs such that continued participation in the study would not be in the best interest of the subject.
- The subject meets an exclusion criterion

Other reasons for withdrawal:

Inability to contact the patient

Handling of Subject Withdrawals

If a patient withdraws from the study, then their record on REDCap will be closed and no further data will be collected. All data collected until that timepoint will be retained and these patients will be included in baseline analyses and reports.

SAFETY CONSIDERATIONS

There are no anticipated safety considerations relating to the WOLVERINE study. There is no risk of harm to either patients or investigators.

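### The withdrawal rule keeps patients found to meet an exclusion criterion in the baseline analyses, and no check of eligibility against the completed operation is named

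*Protocol*

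**What the plan says.** Under Patient Withdrawal, the subsection Reasons for Withdrawal lists the grounds on which an investigator may end a patient's participation. One of them is "The subject meets an exclusion criterion". The next subsection, Handling of Subject Withdrawals, gives a single rule. The REDCap record is closed, collection stops, and then: "All data collected until that timepoint will be retained and these patients will be included in baseline analyses and reports". Patients who leave by choice and patients who should not have been in the study are not separated.

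On timing, a footnote in the identification and consent section says "Ideally, potential participants will be identified pre-operatively". The Process for consent for follow-up has eligibility judged before the study is discussed. The paragraph on patient-reported outcomes under Data Management allows consent before or after surgery.

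The Eligibility section requires an incision of at least 5 cm, extraction sites included. Three exclusions describe the operation itself: "Patients undergoing incisional, ventral, umbilical, and inguinal/femoral hernia repair", "Simultaneous hyperthermic intraperitoneal chemotherapy (HIPEC) and/or cytoreductive surgery" and "Stoma reversal without additional laparotomy incision".

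Two places describe checks on incoming forms: Data Management (under Data Handling and Record Keeping) and Monitoring. Both cover missing data, inconsistencies and protocol compliance. Neither mentions eligibility or says how a patient found ineligible is to be analysed.

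**The concern.** Keeping the data of an eligible participant who withdraws is good practice, because dropping such patients could bias the description of the cohort. The same rule is wrong for someone who never belonged to the target population. Here one sentence covers both groups, so the baseline description can include operations that the Eligibility section rules out.

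The study has a route by which this can arise. A patient can be judged eligible in clinic, consent, and then have an operation that differs from the one planned. For example, a stoma reversal planned with a laparotomy may be completed without one, or cytoreduction may be added. At stake is the denominator of the baseline tables and possibly of the closure and infection-prevention summaries.

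**Working it through.** No stated figure is in dispute. The cohort size of 1,000 is a feasibility projection, and the point does not depend on it. The check is one of reading, followed by an illustration of scale.

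**Reading the text**

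1. *Can a patient be enrolled before eligibility is settled?* Yes. Pre-operative identification is preferred and consent may precede surgery. Final incision length and changes made in theatre are known only at operation.
2. *Is eligibility confirmed afterwards?* No such step is named. The screening, consent and follow-up sections describe none, and the form checks are general.
3. *What happens to a patient found to meet an exclusion criterion?* The investigator may, but need not, end participation. If participation ends, the case falls under withdrawal, and the only rule there places the patient in the baseline analyses.
4. *Does this reach the practice summaries?* Possibly. Data Management groups pre-operative and intra-operative data together as index-admission data, and the list of collection times gives only baseline and 30 days at surgeon level. On that reading, closure data are baseline data. The Schedule of Events, however, puts surgery information under a post-surgery column, separate from the baseline column.

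**Illustration of scale (all rates assumed)**

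Let f be the share of ineligible patients in a table, p the rate of a practice in eligible patients and q its rate in ineligible patients.

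- Observed rate = (1 − f)p + fq, so the shift is f(q − p).
- 95% half-width with N = 1,000 is 1.96 × √(p(1 − p)/N).

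For a rare practice, take p = 5% and q = 80%, for example mesh use if the ineligible operations were hernia repairs. The half-width is 1.96 × √(0.05 × 0.95/1,000) = 1.35 points. For a common practice, take p = 50% and q = 80%. The half-width is 1.96 × √(0.5 × 0.5/1,000) = 3.1 points.

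| f | Rare: observed rate | Rare: shift (points) | Common: observed rate | Common: shift (points) |
|---|---|---|---|---|
| 1% | 5.75% | 0.75 | 50.3% | 0.3 |
| 2% | 6.5% | 1.5 | 50.6% | 0.6 |
| 5% | 8.75% | 3.75 | 51.5% | 1.5 |
| 10% | 12.5% | 7.5 | 53.0% | 3.0 |

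With q = 20% the common-practice shifts have the same size and the opposite sign. The rare-practice columns are deliberately unfavourable, since a planned hernia repair should be recognised before enrolment. With q = 50% instead of 80%, the shift at f = 2% is 0.02 × (0.50 − 0.05) = 0.9 points. With q = 0 it is −0.1 points.

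**The case against.** The strongest reply has four parts.

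*Identification is not enrolment.* The footnote concerns potential participants, and there is a screening log. The consent section ties access to eligibility: "This unique identifier will be recorded on the WOLVERINE PIS. Eligible patients will also be provided with a generic QR code". Patients may also be identified and consented during or after surgery. This narrows the route but does not close it, because a patient can be eligible as planned and ineligible as operated.

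*Form checks exist.* Data staff and the Data Management Committee could notice an excluded operation. That stands as a means of detection. It does not settle the analysis, because once the patient is detected the only written rule is the retention rule.

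*The handling paragraph may mean patient-initiated withdrawal only.* Its opening words allow this, but it directly follows a list that includes investigator termination and inability to contact. On the narrow reading, patients found ineligible have no handling rule, which still needs a sentence.

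*Analysis sets belong in the statistical analysis plan.* Usually so, and one is promised. Here the protocol already states that these patients are counted, so the later plan would have to override it.

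A reader might also infer more than the text supports:

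- That eligibility as a whole is unknown until surgery ends. Planned hernia repair, planned HIPEC or cytoreduction, planned stoma reversal without laparotomy, and lack of email or internet access are ordinarily known beforehand.
- That the rule places incisions under 5 cm in the tables. Such a patient fails an inclusion criterion, which the exclusion-criterion ground does not name. Patient Identification and Consent restricts inclusion to those who meet the criteria, and the sample size section also speaks of eligible patients. The gap there is the missing confirmation step.
- That the practice tables are certainly contaminated. The Schedule of Events leaves this open, and the Rationale for study design assigns the description of worldwide practice variation to the parallel audit.

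**Conclusion.** The point holds as a defect in a stated rule. Meeting an exclusion criterion is treated as a withdrawal, and the single handling rule puts withdrawn patients into the baseline analyses. No confirmation of eligibility against the completed operation is named that would catch such patients earlier.

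The size cannot be derived from the documents, which give no rate of ineligibility and no practice rates. It is probably small, since the rule reaches only patients enrolled and later found to meet an exclusion criterion, and most exclusions are visible before surgery. On the assumed values, common practices move by no more than 3.0 points even at 10% ineligible. A rare practice concentrated in the excluded operations could move by about its own half-width at 2% (1.5 against 1.35 points). The effect on closure and infection-prevention summaries depends on intra-operative data counting as baseline, which the protocol does not settle. The point deserves correction because the remedy is cheap, not because a large bias has been shown.

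**What to change.** 1. In Handling of Subject Withdrawals, limit the retention rule to eligible participants who withdraw.
2. Add a required confirmation to the post-operative REDCap form: the completed operation meets the inclusion criteria, including an incision of at least 5 cm, and no exclusion criterion applies.
3. Class patients who fail this as found ineligible, not as withdrawn. Count them in the flow diagram and leave them out of the baseline and outcome analyses.

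The cost is one protocol sentence, one form field and a slightly smaller analysed count. Precision hardly changes. If 2% of 1,000 were removed, 980 remain, and the half-width for a 5% rate becomes 1.96 × √(0.05 × 0.95/980) = 1.36 points instead of 1.35.
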